diagnosis of sleep disorder [in order to avoid ceiling effects due to disrupted sleep]; (4) Allergy to any of the foods in the food buffet [to guard participant safety].

Recruitment strategies will consist of a variety of methods including online postings, some targeted to specific demographics to match our planned enrollment table (for example, Facebook offers specification of populations for ads to reach), physical flyers around the UCLA community, listings on clinicaltrials.gov, clinicaltrials.ucla.edu, and other study recruitment portals such as researchmatch.com, and the psychology subject pools for our university. We have found in the past that recruiting to match the demographics of LA County is not difficult for White, Asian, and Latinx populations. However, recruiting 9% African American participants may be a challenge. Therefore, we will activate our existing database of churches and beauty salons/barber shops that enabled us to successfully recruit a 50% African-American sample in a prior study funded by the Robert Wood Johnson Foundation. We will also conduct in-person recruitment at community centers and events in areas represented by a large proportion of ethnic/racial minority individuals.

The cover story for this study will be that we are studying the relationship between health habits and consumer preferences. This cover story ties together the disparate elements of the study, including the health behavior measurement and taste test task. All participants will be scheduled between 3:00 and 5:00 pm. This time frame was chosen because we want the manipulation to occur late in the day to be proximal to sleep, but not so late that dinnertime hunger levels create ceiling effects for eating.

All participants will provide written, informed consent. Eligibility will be confirmed by measuring potential participants' weight and height in the lab. The other inclusion/exclusion criteria will be confirmed through a questionnaire. Participants will complete the resilience measures. They will then be given instructions on actigraph use and will affix the physical activity actigraph to their leg (the sleep actigraph is a wrist device that they will put on like a normal watch before sleep). They will also be trained on the food diary, along with serving size estimation training [1], [2]. To ascertain that the participants have successfully understood how

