will use the Emotion Regulation Questionnaire subscale that captures habitual cognitive reappraisal [9]. A sample item is, “I control my emotions by changing the way I think about the situation I’m in,” administered on a Likert scale where 1 = Strongly disagree and 7 = Strongly agree. To measure emotional support, we will use the Patient-Reported Outcomes Measurement Information System (PROMIS) [10] emotional support scale [11]. A sample item is, “I have someone who will listen to me when I need to talk,” administered on a Likert scale where 1 = Never and 5 = Always. To measure emotional approach coping, we will use the coping through emotional approach scale [12]. A sample item is, “I let my feelings come out freely,” administered on a Likert scale where 1 = I usually don’t do this at all and 4 = I usually do this a lot. A sense of social belonging will be measured with the General Belongingness Scale [13]. A sample item is “I feel connected with others,” administered on a Likert scale where 1 = Strongly disagree and 7 = Strongly agree. The tendency to engage in self-affirmation will be measured with the Spontaneous Self-Affirmation Measure [14]. A sample item is, “When I feel threatened or anxious by people or events I find myself thinking about my values,” administered on a Likert scale where 1 = Disagree completely and 7 = Agree completely. Group identification will be assessed using the Leach In-Group Identification Measure [15]. A sample item is, “The fact that I am heavier is an important part of my identity,” administered on a Likert scale where 1 = Strongly disagree and 7 = Strongly agree.

Before and after the randomization to condition, we will measure 3 days of physical activity, sleep, and self-reported eating behavior (we will also have an objective measure of eating; see below). We carefully considered the length of this assessment period. Too short and the health behaviors may not be captured reliably. Too long and the effects of the manipulation may not be detectable across several days. Thus, the assessment period of 3 days was chosen because it represents a balance between reliable measurement of health behaviors and feasibly capturing the effects of our manipulation. Moreover, 3 days would represent the longest existing follow-up, to our knowledge, of experimental effects of weight stigma or indeed any form of social stigma. Therefore, this study is anticipated to have high impact on the field.

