Eating: We will use objective and self-reported measures of eating behavior. We chose the tasks we describe next based on the expertise of PI [name] and Co-I [name], who have extensive

experience measuring eating behavior in the lab and outside of the lab. In the 3 days pre- and post-manipulation, participants will self-report their food intake using food diaries [16] that were designed by a registered dietitian [1]. To control for weekday/weekend variability in diet [17], we will ensure that the pre- and post- manipulation days will have the same makeup (all weekdays, 1 weekend day, 2 weekend days). This may necessitate a gap between their baseline 3-day measurement and their lab visit for the manipulation, but follow-up measurement will begin immediately after the manipulation. These food diaries will be coded using Nutrition Data System for Research (NDSR) software (University of Minnesota Nutrition Coordinating Center). Our primary eating outcome for the food diaries will be kilocalories because calories drive obesity, although exploratory analyses will be conducted using macronutrients such as % sugar and % trans fat, as these are foods recommended to be avoided according to the 2015-2020 USDA Dietary Guidelines for Americans [18]. Adherence to food diaries will be maximized by providing daily reminders, and monitoring the diaries remotely to nudge those who are not completing them.

Given known weaknesses with self-reported food intake [19], we will also objectively measure food intake in the lab. Food consumption of the following items will be measured: Cookies, chocolate candies, potato chips, and Sprite. These foods were chosen because the 2015-2020 USDA Dietary Guidelines for Americans recommend limiting foods with saturated fats, trans fats, added sugars, refined starches, and sodium [18]. To avoid floor effects that can threaten the validity of laboratory eating paradigms, the eating will take place under the guise of a “consumer preferences” faux taste test task [20]. Participants will be asked to rate each of the foods for taste, texture, etc. To avoid ceiling effects and to allow participants to eat without fearing that the experimenter will negatively judge the amount they have eaten, large quantities of each food will be made available.

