Descriptive statistics will be generated for the demographic, mediating, and outcome variables, in aggregate and by randomized assignment (weight stigma vs. control). Eating behavior is often skewed, and if kilocalorie intake evinces skew greater than 3.0 we will conduct transformations (either square root or natural-log) to normalize the data. In addition, all other variables with skew greater than 3.0 will be natural-log transformed. Cronbach's α will be computed to confirm internal consistency for self-reported outcomes. Values will be averaged over the 3 pre- and post-manipulation days, respectively. With this randomized study, intention to treat analysis will be performed to ensure causal inference. Analysis of variance will test main effects of the weight stigma manipulation on the outcome measures. As we are utilizing randomization, we do not anticipate a priori that covariates will be necessary. However, we will test for potential failure of randomization and include necessary covariates in the models.

Moderation analyses to test resilience buffering will be conducted using the PROCESS macro, Model 1 [24], testing whether the effect of the weight stigma condition on the three outcomes is moderated by the resilience variables. We will additionally control for exposure-outcome (e.g., socioeconomic status, operationalized as recommended by the MacArthur Network on SES and Health [25]) and moderator-outcome (e.g., depression, measured by the Center for Epidemiologic Studies Depression Scale [26]) confounding. As we are engaging in primary data collection in the laboratory, missing data will occur at relatively low levels in our experience. However, in consultation with Co-I/Biostatistician [name], we will use missing data/imputation methods if necessary.

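### Averaging the three follow-up days before an ANOVA hides any fading of the effect and leaves lost days without a rule; a day-level mixed model keeps the same primary contrast and addresses both, if days are missing at random

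*Combined protocol and SAP*

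**What the plan says.** The Statistical Analysis Plan reduces each repeatedly measured outcome to one value before and one after the manipulation: "Values will be averaged over the 3 pre- and post-manipulation days, respectively". The test is then "Analysis of variance will test main effects of the weight stigma manipulation on the outcome measures". No day factor, condition-by-day term or weekday/weekend term is planned. The text does not say how the baseline mean enters. Aim 1 speaks of changes in behaviour, but the SAP expects no covariates unless randomisation appears to have failed.

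Three statements in the Methods bear on this:

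- On the length of the assessment period: "Too long and the effects of the manipulation may not be detectable across several days".
- On visit times, among the reasons for the late-afternoon slot: "we want the manipulation to occur late in the day to be proximal to sleep".
- On weekday/weekend variation, under Eating: "we will ensure that the pre- and post- manipulation days will have the same makeup". This is achieved by scheduling alone.

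On the analysis set and missing data, the SAP says that "intention to treat analysis will be performed to ensure causal inference", that "missing data will occur at relatively low levels in our experience", and that "we will use missing data/imputation methods if necessary". It names no imputation method, no trigger for using one, and no minimum number of valid days for a mean.

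**The concern.** The design collects daily data around a single brief exposure, and the protocol itself raises the possibility that the effect will not last. Once the days are averaged, an effect that is large on day 1 and gone by day 3 looks the same as a smaller constant one. If the averaged result is null, nothing prespecified separates no effect from a short one, and any day-level analysis added later would be post hoc.

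The second issue is lost diary or wear days. A mean over the remaining days no longer has the weekday/weekend makeup that the scheduling was meant to secure for that person. If the chance of losing later days depends on what happened on earlier days, means over available days or complete cases can also be biased between arms. The SAP leaves the remedy open, so the choice would be made after the pattern of missing data is known.

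**Working it through.** **Inputs from the documents.** The target is 300 participants with equal allocation, so 150 per arm. The dropout allowance is 300 × 0.10 = 30, giving the stated 330 (330 × 0.9 = 297, close to the target). The available text gives no power figure for the main effect, so there is none to reproduce; the sample size is argued from the moderator-by-condition interaction.

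**Assumptions not in the documents.** Two-sided 5%, effects in one-day SD units, equal correlation ρ between days, no covariates.

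**Step 1: power under fading.** Power ≈ Φ(effect/SE − 1.96), with these standard errors at ρ = 0.4:

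- 3-day mean: √((1 + 2ρ)/3) × √(2/150) = 0.7746 × 0.1155 = 0.0894
- Day 1: √(2/150) = 0.1155
- Day 1 minus day 3 (linear trend): √(2(1 − ρ)) × √(2/150) = 1.0954 × 0.1155 = 0.1265

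| Daily effects (SD) | Contrast | Effect/SE | Power |
|---|---|---|---|
| 0.30/0.30/0.30 | 3-day mean | 0.30/0.0894 = 3.35 | 92% |
| 0.30/0.30/0.30 | Day 1 | 0.30/0.1155 = 2.60 | 74% |
| 0.30/0.15/0.05 | 3-day mean | 0.1667/0.0894 = 1.86 | 46% |
| 0.30/0.15/0.05 | Day 1 | 0.30/0.1155 = 2.60 | 74% |
| 0.30/0.15/0.05 | Linear trend | 0.25/0.1265 = 1.98 | 51% |

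Under the fade, power for the mean is 56% at ρ = 0.2 and 39% at ρ = 0.6.

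**Step 2: does the model change the primary contrast?** On one complete simulated data set, ANOVA on 3-day means gave 0.1909 (SE 0.0873). A random-intercept model averaged equally over days also gave 0.1909 (SE 0.0873). Before covariates are added, estimate and power are the same, so only the added day contrasts reveal a fade.

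**Step 3: a lost weekend day.** With a weekend shift of w and one weekend day in the window, losing that day moves the person's mean by w/3. For w = 0.2 to 0.5 SD this is 0.07 to 0.17 SD. Between arms, the shift is w/3 times the difference in loss rates: zero if loss is equal, and 0.007 to 0.017 SD for a 10-point difference.

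**Step 4: bias from lost days.** These are 400 simulated trials per mechanism, with ρ = 0.5, a fade of 0.4/0.2/0 (true average 0.20 SD), and a mixed model on post-manipulation days only with a weekend term. The weekend shift is 0.35 SD, and also 0.5 SD in the second row.

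| How days are lost | Available-day means | Complete cases | Mixed model |
|---|---|---|---|
| At random, 15% each of days 2 and 3 | +0.016 | -0.001 | -0.001 |
| 20-point arm difference in weekend loss | -0.020 to -0.027 | -0.026 to -0.030 | -0.004 |
| Stigma-arm loss of days 2 and 3 depends on day 1 | +0.141 | -0.215 | +0.002 |
| Stigma-arm loss depends on that day's unseen value | -0.201 | -0.454 | -0.218 |
| No post day (13% overall; in the stigma arm related to own level) | -0.103 | -0.103 | -0.102 |

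**Step 5: participants with no follow-up day.** A separate simulation (2,000 runs, correlation 0.5, no true effect) had about 14% stigma-arm dropout that depended on baseline level. The unadjusted comparison of post means was biased by -0.083 SD. Conditioning on the baseline mean gave 0.001 SD.

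**The case against.** The strongest reply is that a 3-day mean is a valid summary measure that fits the protocol's own compromise between reliability and persistence. The central hypothesis concerns whether stigma harms everyday behaviour, and its time course is not part of that hypothesis. Under a constant effect the mean is better than day 1 alone (92% against 74%). For eating, the in-lab intake measure already captures an immediate effect. All of this stands, and it is why the 3-day average should remain primary.

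It is also true that the day contrasts would not always settle a null mean. Under the fade at ρ = 0.4, given a non-significant mean, the trend is significant 51% of the time and day 1 about 55%; the 2-df condition-by-day test has 41% power. This limits the gain but does not remove it.

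Two stronger readings are tempting. A reader might infer that averaging contradicts the intention-to-treat statement, or that people with missing days will be dropped. The documents support neither. Intention to treat concerns analysing people as randomised, and the SAP allows imputation; the gap is that it fixes no method. A reader might also infer serious between-arm bias from the broken weekday/weekend match. Step 3 shows that it is small unless loss differs by arm, and the documents do not suggest that it will. They describe reminders, remote diary monitoring and payment by day, and they expect little missing data.

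Finally, the model does not suit every measure, and the moderation analyses are specified separately through PROCESS. Both points stand as limits of scope.

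**Conclusion.** The point holds in limited form. As planned, the analysis cannot distinguish a fading effect from a smaller constant one, and it has no fixed rule for lost days. The cost of fading to the averaged test could be large: 92% power down to 46% in the illustrated case, and 39% to 56% over correlations of 0.2 to 0.6. The mixed model does not recover that power; it only makes the fade visible through secondary contrasts.

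For lost days the gain is real under missing at random (+0.002 SD against +0.141 and -0.215 when loss depends on day 1). It is absent when loss depends on unseen values. A person with no follow-up day gains nothing from a model of post-manipulation days alone; the baseline must be brought in, and even then missing at random is assumed.

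The effect sizes, correlations, weekend shifts and loss mechanisms are all assumptions, because the available text gives none of them. Higher dropout in the stigma arm is a possibility to guard against, with no support in the documents as an expectation.

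**What to change.** For outcomes with daily values before and after the manipulation (diary kilocalories, activity, actigraphy sleep), replace the ANOVA on means by a linear mixed model on the daily values of all randomised participants:

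- **Terms:** condition, day (1 to 3), condition-by-day, a weekend-day indicator, the stratification factors (gender, race/ethnicity) and a participant random intercept.
- **Baseline, used in one way only:** either the baseline mean as a covariate, or the baseline days in the outcome vector with the arms constrained equal at baseline. The second also retains participants with no follow-up day.
- **Primary contrast:** the condition effect averaged equally over days 1 to 3, as now.
- **Secondary, prespecified:** the condition-by-day trend and the day-1 (first-night) contrast, with a note that their power is moderate (about 51% and 74% in the illustrated fade).
- **Missing data:** state a valid-day rule and the missing-at-random assumption, and add one sensitivity analysis that assumes worse outcomes for stigma-arm dropouts.

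The single-occasion in-lab intake measure is outside this change. The sleep diary is described only for the 3 mornings after the lab session, so it would use the model without a baseline term. The SAP should also say whether its skewness transformations apply to daily values, and which form of the outcome the moderation models use.

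The cost is SAP wording, a little more analysis work and two extra contrasts that must be labelled secondary. No new data are needed.

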aims that capitalize on our deep experience manipulating weight stigma in laboratory experiments and our demonstrated expertise in ecological momentary assessment and actigraphy studies. This research will provide a fundamental understanding of weight stigma to potentially identify a future intervention target to ameliorate unfavorable health consequences for the hundreds of millions of Americans at risk for weight stigma, obesity, and cardiovascular disease.

Aim 1: Test the causal effects of weight stigma on diet, physical activity, and sleep in everyday life—we will randomly assign participants to a weight stigma vs. control manipulation and measure changes health behaviors in their everyday lives (3-day diet as captured by EMA food diaries, objectively measured physical activity captured by 24-hour actigraphy, and sleep, captured objectively by overnight actigraphy and subjectively self-reported sleep measures).

Aim 2: Identify resilience factors that confer protection against the causal effects of weight stigma—we will test moderators drawn from two sources of theory (identity/belongingness and stress/coping).

Design

Our approach consists of a one-way between-subjects experimental design, randomizing participants to weight stigma vs. control. We will measure immediate effects on objective eating behavior, and in addition engage in EMA to measure diet, physical activity, and sleep using actigraphy for 3 days pre- and post-manipulation.

Methods

Inclusion criteria are as follows [with justification in brackets]: (1) Age 18 and older [because children do not largely make their own diet/eating choices]; (2) BMI 28 or above [because heavier individuals are those who are most at risk for weight stigma and our preliminary data demonstrate our manipulation is effective in those with BMI 28 or higher]; (2) English-speaking [as the interaction task takes place in English]. Exclusion criteria include: (1) Recent (<1 year) diagnosis of major mental disorders including any eating disorder, mood disorder, schizophrenia, or PTSD [because weight stigma manipulations may impose undue risk for those with these conditions]; (2) Recent (<1 year) diagnosis of major physical conditions that limit physical movement [in order to avoid floor effects due to lack of physical activity]; (3) Recent (<1 year)

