to estimate portion sizes, all participants must pass a pop quiz estimating serving sizes with real food in varying portions.

Participants will then undergo 3 days of food diaries to capture baseline food intake and 3 days of actigraphy to capture baseline sleep and physical activity. Then, participants will return to the lab to undergo the weight stigma or control manipulation. After the manipulation, participants will taste and rate a variety of snack foods under the guise of a Consumer Preferences task (our measure of objective food intake).

They will then undergo another 3 days of food diary and actigraphy measurement. Finally, they will return to the lab, at which point they will return the devices and receive compensation. They will be fully debriefed, which will include a funneled debrief to probe for suspicion of the manipulation.

Our team is deeply committed to engaging in ethical research that protects participant welfare. Across the entire time that the PI has been utilizing weight stigma manipulations, zero adverse events have occurred. Moreover, a peer reviewer for the PI's first weight stigma manipulation (developed with Co-I [name]) noted: "The manipulation that was developed to create this active stigma context was a considerable strength, as it was grounded in theory and effective without crossing ethical boundaries—something that is challenging when designing weight stigma studies." All research will receive human subjects approval from the UCLA Human Research Protection Program. We also have an extensive debriefing protocol in place.

Weight stigma will be manipulated using a protocol we have successfully used previously [3] in which participants are led to believe that their interaction partner (always a trained confederate) endorses anti-fat attitudes. Participants will be told that they will complete consumer rating tasks, some with partners and some alone (to bolster the overall cover story). Participants will complete a "Getting to Know You Questionnaire" to ostensibly exchange with their "partner" (the trained confederate) before meeting in person to conduct the rating task. The questionnaire asks about demographic information (age, gender, and ethnicity) and attitudes toward several groups including "fat people." We will then deliver the confederate's questionnaire to the participant.

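### The Aim 1 analysis does not say how the 3-day baseline is used; pre-specified ANCOVA on it would gain precision from data already being collected

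*Combined protocol and SAP*

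**What the plan says.** Methods provides for "3 days of food diaries to capture baseline food intake and 3 days of actigraphy to capture baseline sleep and physical activity", followed by 3 more days after the manipulation. Under Eating, the protocol matches the weekday/weekend mix of the two periods ("we will ensure that the pre- and post- manipulation days will have the same makeup") and accepts a possible gap before the lab visit to achieve it.

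The first paragraph of the Statistical Analysis Plan reduces each period to a mean: "Values will be averaged over the 3 pre- and post-manipulation days, respectively". The Aim 1 test is then given as: "Analysis of variance will test main effects of the weight stigma manipulation on the outcome measures". On adjustment it states that "we do not anticipate a priori that covariates will be necessary", and continues: "However, we will test for potential failure of randomization and include necessary covariates in the models".

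Two other places bear on the choice of dependent variable. Design says: "Our approach consists of a one-way between-subjects experimental design". Aim 1 says the study will "measure changes health behaviors in their everyday lives".

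For the moderation models, socioeconomic status and depression are given as examples of covariates. The baseline value of the outcome is not named.

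**The concern.** The plan collects, pays for and day-matches a baseline, averages it, and then does not say what it is for. At least three analyses fit the words:

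- ANOVA on the post mean, which suits the one-way between-subjects description but leaves the baseline unused.
- ANOVA on the change, which suits the Aim 1 wording about changes.
- The condition main effect in a pre/post repeated-measures ANOVA, which is a literal reading of main effects but averages in a period the manipulation cannot have affected.

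These have different power, and the choice is open for three outcome domains. None is the most efficient use of the data.

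The conditional-covariate sentence does not fill the gap. It is triggered by chance imbalance, whereas the value of a baseline covariate depends on how well it predicts the outcome. It also names no variables and no threshold.

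What is at stake is precision and pre-specification, not bias: under randomization the unadjusted test has valid type I error.

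**Working it through.** **Inputs from the documents.** 300 analysed participants (330 recruited) and equal allocation, so 150 per arm. The SAP gives no power figure for the Aim 1 main effect, so there is none to reproduce. The 300 comes from interaction simulations in Table 2, which is not in the available text; its absence is not held against the plan.

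**Assumptions, not in the documents.** Two-sided alpha 0.05; d = 0.30 in units of the post-mean SD; equal pre and post SD; correlation r = 0.3, 0.5 or 0.7 between the 3-day pre and post means.

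**Formulas.** Power comes from the noncentral t distribution with noncentrality δ√(150/2), where δ is the standardized effect:

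- Post-only: δ = d, 298 df.
- Change score (the same test as condition × time in a 2×2 mixed ANOVA): δ = d/√(2(1−r)), 298 df.
- ANCOVA: δ = d/√(1−r²), 297 df.

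At r = 0.5, for example, ANCOVA has δ = 0.30/√0.75 = 0.346, against 0.30 for both post-only and change.

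**Power at d = 0.30.**

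| r | Post-only | Change | ANCOVA | Gain over post-only (points) | Gain over change (points) |
|---|---|---|---|---|---|
| 0.3 | 73.6% | 59.0% | 77.5% | 3.9 | 18.4 |
| 0.5 | 73.6% | 73.6% | 84.9% | 11.3 | 11.3 |
| 0.7 | 73.6% | 91.7% | 95.2% | 21.7 | 3.5 |

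**Detectable d at 80% power (r = 0.3/0.5/0.7).** Post-only 0.325 throughout; change 0.384/0.325/0.251; ANCOVA 0.310/0.281/0.232.

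**Sensitivity.** At d = 0.20 the ANCOVA gain over post-only is about 3/11/27 points; at d = 0.40 it is 2/5/7. At r = 0.1 and d = 0.30 it is 0.4 points.

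**Direction.** ANCOVA variance is (1−r²) times post-only variance (0.91/0.75/0.51) and (1+r)/2 times change-score variance (0.65/0.75/0.85). Both factors are below 1 for every r strictly between 0 and 1, so only the size of the gain depends on the assumed r.

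**Repeated-measures main effect.** Averaging pre and post halves the effect, and the average has SD √((1+r)/2), so δ = d/√(2(1+r)). At d = 0.30 power is 36/32/29%.

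**Conditional-covariate route.** The SAP gives no test or threshold, so a baseline t test at 0.05 was assumed: ANCOVA if significant, otherwise post-only. In 40,000 simulated trials per r, the baseline was added in about 5% of trials. Power was 73.4/74.2/75.6%, against 73.1/73.2/73.5% for post-only and 76.9/84.5/95.3% for ANCOVA always. This route recovers only 0.3 to 2.1 points.

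**Moderation models.** With baseline as the only added predictor, the interaction standard error is multiplied by √(1−r²) = 0.95/0.87/0.71. No interaction power is computed, for want of Table 2.

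**The case against.** The strongest reply is that post-only ANOVA may not be what the authors intend. One-way between-subjects describes the randomized factor, not the dependent variable. The Aim 1 wording, the day matching and the averaging of pre values all suggest the baseline will be used, probably as a change score. On that reading the gain at d = 0.30 is 18/11/4 points, falling to 0.7 at r = 0.8. No single r gives a large gain over both alternatives. This stands as a limit on size. It does not remove the point, because the text still does not choose and ANCOVA is the better test on either reading.

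Other objections stand in part:

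- d and r are assumed. The permitted gap before the lab visit and the error in self-reported intake could lower r. The SAP expects effects larger than in its preliminary studies, which would shrink the gain over post-only.
- The moderation factors are a best case, because the moderator, socioeconomic status and depression are already in those models. If these explained 10% of both pre and post values in the same way (an illustration), the partial correlation would be (r−0.1)/0.9 and the factors about 0.975/0.90/0.745.
- The 5% inclusion rate follows from the assumed balance test.
- A complete-case ANCOVA would drop participants with no baseline. The SAP expects little missing data and allows imputation, so this needs a line of text but is not a reason against adjustment.

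**Conclusion.** The concern holds, as a free improvement. The SAP does not say how the day-matched baseline enters the Aim 1 test, and its covariate sentence would seldom bring it in. The direction is certain for any r strictly between 0 and 1. The size is not: at d = 0.30 with 150 per arm, about 4 to 22 points of power over post-only and 18 to 4 over change scores as r goes from 0.3 to 0.7. The planned test remains unbiased, and no power shortfall for Aim 1 is shown. The point covers only outcomes with their own baseline: diary kilocalories, METs and actigraphic sleep. The benefit to the interaction tests, which the SAP calls its lowest-powered, is real but smaller than the best-case factors suggest.

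**What to change.** Replace the ANOVA sentence for the outcomes that have a baseline with:

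> For diary kilocalories, METs and each actigraphic sleep measure, condition will be tested by ANCOVA on the 3-day post-manipulation mean, with the same variable's 3-day pre-manipulation mean as a pre-specified covariate, whatever the randomization check shows.

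Name the same baseline covariate in the moderation models for those outcomes. State that the lab taste test and the morning sleep diary, for which no baseline of the same measure is described, keep the unadjusted comparison. Add that a missing pre mean falls under the SAP's imputation provision, and that the pre mean is transformed in the same way as the post mean if the skew rule applies.

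The cost is SAP wording, settled before unblinded analysis, and one degree of freedom per model. No participants, visits or measures are added.
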